4. STUDY OBJECTIVES

Primary objective:

Evaluate Bone Mineral Density (BMD) changes at lumbar spine of Greek osteoporotic women from baseline to 12th month from the initiation of Alendronate 70mg once weekly.

Secondary objectives:

Evaluate new vertebral and non-vertebral fragility fractures, hip fractures, treatment compliance, occurrence of back pain and days lost from work due to fracture related back pain from baseline to 12th month from the initiation of Alendronate 70mg once weekly.

Also evaluate the safety of Alendronate assessed by the type, frequency, and severity of ADRs for 18 months after the initiation of study.

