8. TREATMENT PROCEDURES AND STUDY PROCEDURES

This study is designed to follow and observe patients who will initiate treatment with Alendronate 70mg in routine clinical practice. No study-specific treatment will be provided and no additional clinical procedures or assessments will be required as part of this observational study. Patients will be observed for a period of up to 12 months after their entry in the study unless patients discontinue the study or are lost to follow up. Information regarding the clinical management of the patients receiving Alendronate 70mg may be collected whenever available, even after treatment discontinuation.

There are no procedures or changes to routine clinical management of patients. It is anticipated that patients will return to the clinic every month to receive their Alendronate 70mg prescription. Patients will be followed for approximately 6 months after their last visit. Available clinical information obtained for routine clinical practice (including those already recorded on the patient medical records ie, baseline characteristics) will be recorded, including Alendronate 70mg administration, previous and current therapies, medical history (including fracture history), ADRs and serious ADRs and co-morbidities.

Throughout the study, investigators may prescribe any concomitant medications or treatments deemed necessary to provide adequate routine clinical care including calcium and vitamin D supplementation, which will be recorded.

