10. STATISTICAL CONSIDERATIONS

Study Outcomes:

The following outcomes are to characterize/estimate the effectiveness during the first 12 months of treatment with Alendronate.

Primary outcome:

- BMD change (%) at lumbar spine at 6,12 months of treatment measured by DXA

Secondary outcomes:

- the proportion of patients with severe osteoporosis experiencing one or more new vertebral and non-vertebral fragility fractures assessed by spine radiographs regardless of symptoms
- Compliance to therapy, self-reported by patients
- Days lost from work due to fracture-related back pain, self reported by patients

The following secondary outcomes are to characterize the safety of patients during the first 12 months of treatment with Alendronate and during the 6 month follow up period:

- the proportion of patients with ADR to Alendronate
- the proportion of patients with serious ADR to Alendronate

The Full Analysis Set will consist of all enrolled patients satisfying the inclusion/exclusion criteria that receive at least 46 doses - 96% of the 48 that ideally would receive during the study duration- and have a non-missing enrollment date. All analyses will be performed on this analysis set.

Subsets and/or Covariates:

The following variables will be collected at baseline, either directly as part of routine clinical practice, or from medical records when available:

Demographic patient data:

- Educational level
- Patient employment status
- Patient living situation (at home with spouse/family, at home with care/support, at home alone, nursing home)

Medical condition regarding osteoporosis:

- Body mass index (≤ 25 or > 25 kg/m²)
- Age at menopause
- Cause of menopause (natural onset, clinically/surgically induced)
- Height loss since maximal height
- Height loss in centimeters (cm)
- Previous fracture
 - Previous hip fracture
 - Previous vertebral fracture
 - Other previous fractures
- Previous hospitalization for osteoporotic fracture and/or surgical osteoporotic fracture treatment
- One or more falls experienced during the past 12 months
- One or more episodes of immobility experienced during the past 12 months
- Parent fractured hip
- Current smoker
- Former smoker
- Systemic glucocorticoid use
- Secondary osteoporosis
- Alcohol consumption
- Femoral neck BMD T-score
- Lumbar spine BMD T-score
- Total hip BMD T-score

Patient-related:

- Age (years)
- Age group (< 65, ≥ 65 to <75, ≥ 75 years)
- Time since Post Menopausal Osteoporosis (PMO) diagnosis

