- Number of comorbidities
- Any chronic medical condition
- Type of chronic medical condition (diabetes/osteoporosis/hypertension/other)

Sample Size:

A review of published data highlighted that BMD change at lumbar spine at 12 months for postmenopausal women on alendronate 70mg weekly ranges from 3.7%-5.1%.¹³⁻¹⁵

Taking into account the most unfavourable result, which is 5.1%, we will estimate the sample size of our study. We will conduct an observational study which intends to investigate the Lumbar Spine BMD (%) change from baseline to 12 months (single proportion).

Published data estimate that Lumbar Spine BMD increases 5.1% from baseline to 12 months.

We would like to ensure that 95% CI of the Lumbar Spine BMD change (%) is estimated with precision ±2% (i.e. with a margin of error of 2%).

The required sample size would be $n \geq \frac{z^2}{\delta^2} p(1-p) \rightarrow n \geq \frac{1.96^2}{0.02^2} 0.051(1-0.051) \rightarrow n \geq 465$

If we add 10% to compensate for potential loss of subjects, the final number will sum up to $n \geq 512$ patients.

Thus in order to have sufficient precision and compensate for potential loss of subjects the final sample size should be 512 patients.

Data Analyses

This is an observational study for which the analysis will be descriptive in nature and no formal hypothesis will be tested. T test will be used to assess the change in BMD between baseline and end of study measurements. Significance was indicated at $P < 0.05$.

For quantitative parameters (BMD, days lost from work) mean, standard deviation, median, range (minimum and maximum), as well as number of missing data (if relevant) will be displayed. For qualitative parameters (bone fractures) counts, percentages and number of missing data if relevant will be displayed. Treatment compliance for each patient will be calculated as the number of doses study drug was actually taken, with the maximum count being 48. Compliance will be regarded as a quantitative parameter.

In general, missing values will remain as missing, i.e., no attempt will be made to impute missing values and only observed values will be used in data analyses and presentations.

Baseline characteristics will be described. Demographics, medical history and other baseline variables will be summarized as appropriate to the type of data.

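### Compliance is analysed only in women who reach at least 46 of a maximum 48 doses, so the analysis set is selected on the outcome and the result is largely fixed in advance

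*Protocol*

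**What the plan says.** Section 4 of the protocol makes compliance a secondary objective, naming "treatment compliance, occurrence of back pain and days lost from work due to fracture related back pain from baseline to 12th month". Section 10 lists it as a secondary outcome: "Compliance to therapy, self-reported by patients".

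Under Data Analyses, Section 10 fixes the measure: "Treatment compliance for each patient will be calculated as the number of doses study drug was actually taken, with the maximum count being 48". It adds: "Compliance will be regarded as a quantitative parameter". Quantitative parameters are to be summarised by mean, standard deviation, median and range.

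The Full Analysis Set in Section 10 is limited to eligible enrolled women with a recorded enrolment date who "receive at least 46 doses - 96% of the 48 that ideally would receive during the study duration". The section then states: "All analyses will be performed on this analysis set". No other set is defined.

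Three further statements bear on the point:

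- Treatment is once weekly, and the objectives run "from baseline to 12th month from the initiation of Alendronate 70mg once weekly". Section 8 states: "Patients will be observed for a period of up to 12 months after their entry in the study".
- Section 9 says that what was collected before a woman withdrew consent goes into the analysis.
- Section 10 rules out imputation; only observed values are used.

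**The concern.** The rule for entering the analysis set and the outcome are the same quantity, the number of doses, measured against the same 48. A woman who stops after three months, or who misses one dose in four, is removed before compliance is summarised. What remains is a description of the entry rule. The summary would show near-complete compliance in a clinic where most women persisted and equally in one where half stopped early.

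This matters because the study sets out to describe the use of alendronate in routine Greek practice, where stopping and missed doses are a large part of what compliance means. A reader of the report would see a mean close to 48 and could take it as a finding about these patients.

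A lesser matter is the figure 48 itself. It serves both as the maximum count and as the base of the 96% threshold, yet it does not match weekly intake over 12 calendar months.

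**Working it through.** **Inputs.** From Section 10: lower bound 46 doses, upper bound 48, stated threshold 96%, one analysis set for all analyses. From Sections 4 and 8: once-weekly intake, 12 months.

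**1. The plan's own figure.** 46/48 = 0.958, which rounds to the stated 96%. It reproduces.

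**2. Possible values.** With entry at 46 or more and a maximum of 48, the count can be 46, 47 or 48:

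| Doses | Share of 48 |
|---|---|
| 46 | 95.8% |
| 47 | 97.9% |
| 48 | 100% |

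The mean must lie between 46 and 48. The population standard deviation cannot exceed half the range, (48 − 46)/2 = 1 dose, or 1/48 = 2.1%. These bounds need no assumption about adherence, only the plain reading that a dose received is a dose taken.

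**3. How far the reported mean could depart from the true one.** The protocol gives no adherence figures, so these are assumed scenarios.

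*Scenario A: each of 48 doses is taken independently with probability p.* The true mean is 48p. The share qualifying is P(X ≥ 46) for X binomial (48, p), and the reported mean is E(X | X ≥ 46).

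| p | True mean | Share qualifying | Reported mean |
|---|---|---|---|
| 0.98 | 47.0 | 92.9% | 47.2 |
| 0.95 | 45.6 | 56.7% | 46.7 |
| 0.90 | 43.2 | 12.9% | 46.4 |
| 0.80 | 38.4 | 0.2% | 46.2 |

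*Scenario B: a share s stops early with a mean of 23 doses, all below 46; the rest all qualify and average 47.* The true mean is 47(1 − s) + 23s.

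| s | True mean | Reported mean |
|---|---|---|
| 10% | 0.9 × 47 + 0.1 × 23 = 44.6 | 47 |
| 30% | 0.7 × 47 + 0.3 × 23 = 39.8 | 47 |
| 50% | 0.5 × 47 + 0.5 × 23 = 35.0 | 47 |

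The size depends on the scenario. The direction does not: removing everyone below 46 can only raise the mean, or leave it unchanged if nobody falls below.

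**4. The figure 48.** It is reproduced as 12 × 4. On a calendar basis, 365.25/7 = 52.2 weeks. Forty-eight weekly doses cover 48 × 7 = 336 days, and 336/30.4375 = 11.0 months. Against 52, 46 doses are 46/52 = 88.5% and 48 doses are 48/52 = 92.3%.

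**5. Sections 9 and 10 side by side.** Section 9 keeps the earlier data of a woman who withdraws. Section 10 excludes her from every analysis if she leaves before dose 46. Both cannot hold.

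**The case against.** The best counter-argument is about wording. The analysis set speaks of doses a patient *receives*, while compliance counts doses actually taken. Elsewhere the protocol uses *receive* for the monthly prescription, and Section 6 separates prescription from administration. If doses received are doses supplied, self-reported intake in the analysis set could fall below 46. This stands as a caveat on the three-value result. It is the weaker reading, since 46 is an odd threshold for monthly supply and both rules use the same 48. Even under it, a woman whose prescriptions ended early is excluded, and the text would still need correcting.

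A reader might infer four stronger things that the documents do not support:

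- *That nothing at all could be learned about compliance.* The size of the analysis set against the number enrolled would give a rough lower bound on the share reaching 46 doses (eligibility and a missing enrolment date also affect entry), and discontinuations with reasons are collected. It is the planned summary that is uninformative.
- *That 48 is a plain error, or that counts above 48 would be cut off.* It is evidently 12 × 4, in line with monthly prescriptions, and the maximum may simply describe what that scheme allows. The request is only to reconcile it with weekly intake over 12 months.
- *That a raw count misleads because observation times differ.* Within the set as defined this has little force: 46 weekly doses take about 45 weeks, so follow-up hardly varies. It matters once all women are included.
- *That any one true compliance figure is known.* The scenarios above are assumed; only the 46 to 48 bound comes from the text.

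It could also be said that a statistical analysis plan will settle this. But the protocol itself fixes both the measure and the set, so a later plan could repair the outcome only by departing from the protocol.

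**Conclusion.** The point holds. As written, the compliance analysis conditions on the compliance outcome. On the plain reading the reported values are confined to 46, 47 or 48 doses, 95.8% to 100% of 48, with a standard deviation of at most about one dose, regardless of true adherence. If receiving means being supplied, the bound loosens but early stoppers remain excluded. Nothing elsewhere in the protocol repairs this, and the Section 9 rule on withdrawn patients adds a contradiction.

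The mismatch between 48 doses and about 52 weeks is a secondary matter of reconciliation. Because compliance is a descriptive secondary outcome in a study without formal hypotheses, the change should be made, but this point alone does not undermine the study.

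**What to change.** Amend Section 10 as follows:

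1. Analyse compliance in all enrolled women who took at least one dose, as doses taken divided by doses scheduled to month 12. Count doses after a known stop as not taken.
2. Give a second figure over the time each woman was under observation. Show women lost to follow-up separately, so that unknown intake is not filled in against the no-imputation rule.
3. Report the number and proportion who stopped treatment and, where recorded, when.
4. Keep the 46-dose set only as a secondary, adherent-patient set, and say whether its threshold refers to doses supplied or doses taken.
5. Reconcile the 46-dose rule with Section 9 on data from women who withdraw.
6. Reconcile the figure 48 with once-weekly intake over 12 months, and use one denominator throughout.

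The cost is small. Section 6 already provides for prescription, administration and adherence information at monthly visits, so this is mainly wording. One check is needed: the data collection table in Section 14 lists prescription and discontinuation with reasons, but has no explicit row for doses taken or stop date. The eCRF should be confirmed to capture both; failing a stop date, monthly visits would place stopping to within about a month.

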9. REMOVAL AND REPLACEMENT OF PATIENTS

Removal of Patients:

Patients have the right to withdraw fully from the study at any time and for any reason without prejudice to her future medical care by the physician or at the institution. Withdrawal of full consent for this study means that the patient does not wish to or is unable to continue further study participation; patient data up to withdrawal of consent will be included in the analysis of the study. The investigator will discuss with the patient appropriate procedures for withdrawal from the study. Should a patient (or a legally acceptable representative) request or decide to withdraw from the study, all efforts will be made to complete and report the observations as thoroughly as possible up to the date of withdrawal. All information should be reported on the applicable eCRFs.

Replacement of Patients:

Participants who withdraw from the study or lost to follow-up will not be replaced.

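### The 12-month BMD change is estimated only in women with at least 46 of 48 doses and a 12-month scan, so early leavers are lost with their 6-month BMD and the mean can be too high

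*Protocol*

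**What the plan says.** Four statements in the protocol decide who contributes to the 12-month result.

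- **Outcome (Section 10, Study Outcomes).** The primary outcome is "BMD change (%) at lumbar spine at 6,12 months of treatment measured by DXA", so the 6-month scan is part of it.
- **Analysis set (Section 10).** The Full Analysis Set is limited to eligible enrolled women who "receive at least 46 doses - 96% of the 48 that ideally would receive during the study duration", and "All analyses will be performed on this analysis set".
- **Analysis and missing data (Section 10, Data Analyses).** "T test will be used to assess the change in BMD between baseline and end of study measurements". As a general rule, "no attempt will be made to impute missing values and only observed values will be used in data analyses and presentations". No exception is given for the primary outcome.
- **Women who leave (Section 9).** They are not replaced, yet "patient data up to withdrawal of consent will be included in the analysis of the study".

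The sample size adds 10% for loss. Section 8 allows information to be gathered after treatment has stopped, if it happens to be available.

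**The concern.** Two filters act one after the other. The dose threshold comes first and removes almost every woman who stops or leaves early, with all her scans. The observed-values rule then removes any remaining woman who lacks a 12-month scan. A woman who stopped the drug but did return for a 12-month scan is also excluded, because she falls short of 46 doses.

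The resulting mean describes all treated women only if passing both filters is unrelated to BMD response. In routine care that is doubtful. Women who tolerate the drug poorly or gain little early on may be less likely to complete the year, and women who took fewer doses may gain less. Either pattern pushes the reported mean upward. Adding 10% to the sample restores numbers but does nothing about selective loss. The stated aim is to evaluate BMD change in Greek women from the start of treatment, so a mean for near-perfect takers answers a narrower question than the one posed.

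**Working it through.** **1. The plan's own figure.** n = 1.96² × 0.051 × 0.949 / 0.02² = 464.8, so 465. Then 465 × 1.10 = 511.5, so 512. It reproduces. It is used here only for the planned loss of 10% and the evaluable number of 465.

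**2. Which filter removes the early leavers.** The threshold is 46/48 = 95.8% of doses. Counting one dose per calendar week, month 6 corresponds to about 26 doses, and dose 46 falls at 46/52 × 12 = 10.6 months. Counting four doses per month, as the maximum of 48 implies, month 6 gives 24 doses and dose 46 falls at 46/4 = 11.5 months. On either count a woman who leaves at about month 6 is far below the threshold and outside the set. The missing-data rule affects only women with 46 or more doses and no 12-month scan.

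**3. Sections 9 and 10 side by side.** Section 9 says that the data of a woman who withdraws, up to that point, enter the analysis. Section 10 applies every analysis to a set that she cannot enter unless she withdraws after dose 46. Both cannot be followed.

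**4. Size of the bias.** Inputs, all assumed because the protocol gives none of them:

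- SD of the 12-month percent change: 3 to 5 points
- correlation ρ of the 6- and 12-month changes: 0.5 to 0.7
- loss after month 6 logistic in the standardised 6-month gain, with log-odds rising by b per SD lower gain
- loss of 10% (the plan's figure) up to 30%

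With bivariate normal changes, the bias of the mean among women who remain is

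bias = ρ × SD × k,

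where k is the mean standardised 6-month gain of those who remain. By numerical integration:

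| b | loss | k | ρ·SD = 0.5 × 3 = 1.5 | ρ·SD = 0.7 × 5 = 3.5 |
|---|---|---|---|---|
| 0.5 | 10% | 0.049 | 0.07 | 0.17 |
| 1.0 | 10% | 0.091 | 0.14 | 0.32 |
| 1.5 | 10% | 0.122 | 0.18 | 0.43 |
| 0.5 | 30% | 0.143 | 0.21 | 0.50 |
| 1.0 | 30% | 0.253 | 0.38 | 0.88 |
| 1.5 | 30% | 0.327 | 0.49 | 1.14 |

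Simulation agrees: 0.14 to 0.31 at 10% and 0.38 to 0.88 at 30% for b = 1, and up to 0.43 and 1.16 for b = 1.5. In the extreme case, where exactly the lowest early gainers leave, k = 0.195 at 10% and 0.497 at 30%. The bias is then about 0.3 to 0.7 and 0.7 to 1.7 points.

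**5. What the 6-month values can repair.** In the simulation, a regression-type estimate using the 6-month values of all women had a bias of about 0. Run inside the set with at least 46 doses, the same estimate had the full observed-case bias, because the women who left are not in that set.

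**6. Scale.** With 465 women the 95% half-width is 1.96 × 3/√465 = 0.27 points for an SD of 3, and 1.96 × 5/√465 = 0.45 for an SD of 5.

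**The case against.** The strongest objection is that the size is assumed. The protocol gives no SD, correlation or loss pattern, and nowhere says that a poor 6-month scan leads a woman to leave. Intolerance need not be related to BMD gain. The near-zero bias of the model holds by construction, since loss was simulated to depend only on the 6-month value. The 30% scenarios exceed the planned 10%. Apart from the extreme case, every bias at 10% loss is below the half-width for the same SD, and all the biases lie within the protocol's stated ±2% margin. This stands: the figures show what could happen, not what will.

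It is also fair that 6-month scans may be patchy. Section 8 requires no extra assessments and the data collection table in Section 14 has no BMD or DXA row. The analysis is called descriptive, the missing-data rule is worded as a general one, and counts of missing values are already planned. Sensitivity analyses could therefore appear in an SAP. None of this alters the fact that the set, the t test and the observed-values rule are fixed in the protocol and conflict with Section 9.

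Three stronger readings are tempting but unsupported. A reader might infer that the no-imputation sentence is what discards the leavers, so that a mixed model alone would cure the problem; the 46-dose set acts first. A reader might infer that 6-month BMD is ignored altogether; it is a primary time point and can be reported for women in the set. A reader might infer that the 12-month mean is known to be inflated; that depends on who leaves, which the documents do not say.

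**Conclusion.** The point holds. The 12-month mean is restricted by dose count and by scan availability, and this contradicts the protocol's own statement about women who withdraw. If loss is moderately to strongly related to a low early gain, the mean is too high by about 0.1 to 0.4 points at the planned 10% loss and about 0.4 to 1.2 points at 30%; weaker dependence gives less. The range rests on the assumed SD, correlation and loss mechanism.

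Against the ±2% margin this is modest. Against the interval that the study would actually report it is not: at 10% loss the bias with b = 1 to 1.5 is about half or more of the half-width for the same SD, at the less favourable correlation of 0.7 and SD of 5 (0.32 to 0.43 against 0.45). The change should be made, but the study's conclusions do not stand or fall on it.

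**What to change.** 1. **Open the set.** For the BMD analysis, replace the 46-dose set with all eligible women who started treatment and have a baseline and at least one later scan. Reconcile Section 10 with Section 9. Keep the set with at least 46 doses as a sensitivity analysis.
2. **Use every scan.** In place of the observed-case t test, estimate the 6- and 12-month percent change from one repeated-measures mixed model with visit and baseline BMD. Report the observed-case mean as sensitivity, and compare baseline characteristics of women with and without a 12-month scan.

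Step 1 must come first; step 2 alone recovers almost nothing.

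The cost is a little more analysis work, with no new patients or procedures, and possibly a slightly smaller estimated gain. The correction relies on loss being explained by observed values. For women without a 12-month scan it works only if a 6-month scan exists, so the number of such scans should be reported.
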